1.0 Introduction and Background

The radial forearm fasciocutaneous free flap (hereafter referred to as RFFF) was described more than 30 years ago as a fasciocutaneous flap for microsurgical transfer.[1] It was soon after established as a safe and reliable flap for transfer of fascia and cutaneous tissue.[2, 3] Currently, it is used to repair any defect in which a relatively thin island of skin is needed with a fascial strength layer.[4-6] While the flap itself is very reliable, it leaves a donor site that can be very unsightly and has multiple known complications including loss of pronation, pain, paresthesias, cold intolerance, and skin graft necrosis.[7-9] The donor site is typically covered with a split thickness skin graft (hereafter referred to as STSG). In an effort to minimize these complications, several groups have described a technique of placing Integra© dermal substitute (hereafter referred to as Integra) underneath the STSG to provide a thicker support and decrease overall morbidity associated with the defect. These studies have shown success in decreasing overall morbidity including increasing range of motion and improving aesthetic quality of the donor site. However, the largest study to date has included only 29 subjects. Furthermore, these studies do not provide a comparative cohort of subjects repaired with a classic STSG to show effectiveness of this technique when compared to a classic repair.[10-14] Our goal is to perform a prospective study comparing subjects repaired with a classic STSG and those repaired with one step Integra and STSG applied at the same time. These subjects will be evaluated for overall donor site aesthetic quality and functional outcome as described below.

1.1 Primary Objective(s)

Compare donor site aesthetic quality and functional outcomes of subjects with a classic STSG and those repaired with Integra and STSG.

2.0 Subject Selection

This clinical trial can fulfill its objective only if subjects appropriate for this trial are enrolled.

2.1 Inclusion Criteria

- 2.1.1 All subjects who receive a radial forearm free flaps in the included time period, including subjects with head and neck cancer, traumatic defects, chronic wounds, or any other problems that require a radical forearm free flap for reconstruction.
- 2.1.2 Have had a distal, anterograde fasciocutaneous flap
- 2.1.3 Age \geq 18 years
- 2.1.4 All smokers and tobacco users will be included in this study.

2.2 Exclusion Criteria

- 2.2.1 Subjects who have had an osteocutaneous or musculocutaneous flap.

The Use of Integra© in Coverage of Radial Forearm Free Flap Donor Site Defect

Comprehensive Cancer Center of Wake Forest University (CCCFWU)

CCCFWU # 99915A

- 2.2.2 Subjects who have a radial forearm flap with a proximal skin flap or subjects that receive a “reverse” radial forearm flap
- 2.2.3 Pregnant women will be excluded due to the lack of clinical studies evaluating INTEGRA template in pregnant women.

2.3 Inclusion of Women and Minorities

Men and women of all races and ethnicities who meet the above-described eligibility criteria are eligible to participate in this study.

4.0 Registration Procedures

All subjects entered on any CCCWFU trial, whether treatment, companion, or cancer control trial, **must** be registered with the CCCWFU Protocol Registrar or entered into ORIS Screening Log. Subjects **must** be registered prior to the initiation of treatment.

You must perform the following steps in order to ensure prompt registration of your subject:

1. Complete the Reduced Review Registration Form (Appendix A)
2. Complete the Race Verification Form (Appendix B)
3. Send the Reduced Review Protocol Registration Form, and the Race Verification Form to the registrar, either by fax or e-mail.

Contact Information:

Protocol Registrar [contact]

Protocol Registrar [contact]

Protocol Registrar E-MAIL ([contact])

*Protocol Registration is open from 8:30 AM - 4:00 PM, Monday-Friday.

To complete the registration process, the Registrar will:

- assign a subject study number
- randomize the subject
- register the subject on the study

5.0 Study Outcomes and Study Measures

For this study, we will include all subjects that meet the above criteria that are receiving distal, anterograde fasciocutaneous Radial Forearm Free Flaps. For inclusion in the study, only those receiving proximally based flaps with the skin paddle located over the tendons will be included.

Informed consent will be take place in the clinic in a private exam room. After reviewing the consent form and all questions and concerns have been addressed, if the subject or legally

The Use of Integra© in Coverage of Radial Forearm Free Flap Donor Site Defect

Comprehensive Cancer Center of Wake Forest University (CCCFWU)

CCCFWU # 99915A

authorized representative chooses to participate, then a signature will be obtained on the informed consent document.

Subjects will be randomized to either receive both Integra and a STSG or a regular STSG. Consideration of treatment of the donor site will be the same regardless of the final destination of transferred tissue.

The subjects will receive the assigned reconstruction as dictated by the protocol. They will either receive 1) a 0.012mm STSG or 2) A sheet of Integra directly on the wound bed with subsequent removal of the overlying silicone sheet and immediate application of a 0.008mm STSG. The skin grafts will be meshed 1:1 for minimal graft distortion and to avoid variability of "pie crusting." The RFFF donor site will then be covered by a non-adherent dressing, such as Adaptec, and a vacuum assisted closure (VAC) device. The VAC will stay in place for 5 days following surgery, and during this time a simple removable thumb spica splint will be placed to prevent wrist motion. Subjects with free tissue transfer will typically have a 4-5 day hospital admission. The plastic surgery team will follow them during their admission and will schedule appropriate follow up at both one and two weeks following surgery. Follow up appointments following this time will be at the discretion of the attending physician.

Scheduled post-operative assessments following the initial assessment will include a 3 month, 6 month, and one year follow up appointment. Evaluation at the 3-month and 6-month follow-up appointment, will include photos of the surgical site, evaluation of the skin graft and any areas of necrosis or tendon exposure, survey of presence of pain and paresthesia, and the QuickDASH survey. During the 1 year follow-up, in addition the assessments described above, the Vancouver Scale Assessment will be performed by a Co-Investigator who is blinded. Areas of tendon exposure will be treated with xeroform dressing changes.

During surgery and at the scheduled follow up all subjects will have standardized photographs taken utilizing a custom backdrop and a centimeter scale. These pictures will be used to assess wound size and dimension at each encounter, including the original surgery. This will allow us to measure the rate of wound healing, contracture, and rate of skin graft necrosis. The pictures will be analyzed with the SigmaScan planimetry program. This protocol has been previously validated and published.[15]

Subjects will be evaluated by the occupational therapy team prior to their surgery in the pre-operative holding area and during their admission to the hospital. They will be assessed using standard measurement from a goniometer and dynamometer and also given instructions for wrist range of motion exercises. During follow up, subjects will be referred to occupational and physical therapy at the discretion of the attending physician.

Subjects removed from study for unacceptable adverse events will be followed until resolution or stabilization of the adverse event.

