13.0 Statistical Considerations

Endpoints:

1. Rate of tendon exposure. Previously reported from 12-55%. [7, 16-19]
2. Rate and percent of skin graft necrosis. Rate previously reported to be from 7%-51%. [7, 9, 16, 20-22]
Percentage of skin graft loss ranges from $\leq 5\%$ - $\geq 20\%$. [9, 16]
3. Rate of paresthesia. Previously reported to be 36%- 50%. [9, 20]
4. Aesthetic outcome of donor site on Vancouver Scar Scale, a validated objective assessment of scar appearance. [23] Previous scores are reported to be 4.7/13 without Integra and 4.2/13 with Integra. [14, 24]
In particular, we will be focusing on the pliability aspect of the Vancouver Scar Scale, which will be a measure of the functionality of the skin overlying the donor site. The scores will be taken at the 3,6, and 12 month follow up.
5. The Disabilities of the Arm, Shoulder and Hand (DASH) outcome measure is a 30 question survey used to quantify the symptoms and function of any person with musculoskeletal disorders of the upper limb. It is used to determine the impact that a particular disorder has on an individual's life. [25, 26] The QuickDASH is a shortened version of the DASH that has been validated to be as significant as the full questionnaire. [27] While the QuickDash scores of RFFF subjects have not been reported, previous DASH scores have been reported to be 6.93 ± 5.54 in RFFF subjects compared to 2.95 ± 4.42 in non-RFFF subjects. [28]
6. Differences in range of motion at the hand, previously reported to be 22-27 degrees difference [8]
7. Differences in grip and pinch strength in the donor site hand, previously reported to be about a 7kg difference in pinch strength and a 0.75kg difference in grip strength. [29]
8. Wound contracture and Skin Pliability. Normal results are reported below.

Statistical Analysis:

We plan to enroll 50 subjects in each group. All hypothesis testing will two sided and performed at the 0.05 significance level. All analysis will be performed in SAS Version 9.4 (Cary, NC). No interim monitoring is planned for this study.

The analysis and estimated power for each endpoint is described below.

1. Rate of tendon exposure
 - a. We expect about a 25% rate of tendon exposure in the group that does not use Integra, while in the Integra group we hope to have a rate of tendon exposure of below 5%. We will test this hypothesis using a chi-squared test of equal proportions. We will have 81% power to detect this difference with 50 subjects in each group.

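### Donor-site harms outside the listed endpoints (infection, fluid collection, repeat grafting, other unplanned procedures) are not counted by arm, and early graft loss may go uncounted

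*Combined protocol and SAP*

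**What the plan says.** Section 1.0 gives the reason for placing Integra under the graft: thicker support, and to "decrease overall morbidity associated with the defect". Section 1.1 limits the primary objective to donor-site appearance and function.

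Section 13.0 lists eight endpoints: tendon exposure, graft necrosis, paresthesia, the Vancouver Scar Scale, DASH/QuickDASH, range of motion, grip and pinch strength, and contracture with pliability. Its analysis part adds pain. On testing it says "All hypothesis testing will two sided and performed at the 0.05 significance level", and on size "We plan to enroll 50 subjects in each group".

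Section 5.0 gives the content of the visits:

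- **Weeks 1 and 2:** appointments are scheduled, but nothing is listed to be assessed. Visits after that are left to the attending physician until 3 months.
- **Months 3 and 6:** photographs, "evaluation of the skin graft and any areas of necrosis or tendon exposure, survey of presence of pain and paresthesia, and the QuickDASH survey".
- **1 year:** the same, plus a blinded Vancouver Scar Scale.
- **Photographs:** taken at surgery and at scheduled follow-up, and measured by planimetry for healing, contracture and necrosis.

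Adverse events are mentioned once, in section 5.0: "Subjects removed from study for unacceptable adverse events will be followed until resolution or stabilization of the adverse event". Section 6.0 lists two registration forms, survey data and PHI data. It lists no adverse-event form.

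**The concern.** The experimental arm adds a material to the wound bed. A reader weighing its effect on morbidity will ask about infection, fluid under the graft, second grafts and returns to theatre. Followed exactly as written, the plan gives no count of these by arm. The one adverse-event sentence concerns follow-up of subjects who have been removed. It does not define, collect or tabulate events.

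Endpoint 2 has a related gap. If a graft is lost and replaced after the week-2 visit and before month 3, the first evaluation with specified content sees the replacement. Nothing requires the loss or the repeat graft to be recorded, counted as necrosis, or marked when the scar is scored at 1 year.

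**Working it through.** **1. Does any part of the plan count these events?**

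| Place | Covered | Infection, fluid collection, repeat graft, other unplanned procedure |
|---|---|---|
| Section 13.0, endpoints | the eight listed above | none |
| Section 13.0, analyses | the same, plus pain | none |
| Section 5.0, weeks 1 and 2 | no content listed | none |
| Section 5.0, months 3, 6 and 12 | graft, necrosis, tendon exposure, pain, paresthesia, QuickDASH; scar scale at 12 | none |
| Section 6.0, data capture | registration, survey, PHI | none |

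**2. The plan's own power figures.** For tendon exposure: "We expect about a 25% rate of tendon exposure in the group that does not use Integra", against 5% as the upper end of the rate hoped for with Integra, and "We will test this hypothesis using a chi-squared test of equal proportions". With n = 50 per arm and two-sided 0.05, the normal approximation with pooled variance under the null is

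power = Φ{ [ |p1 − p2|√n − 1.96√(2p̄(1 − p̄)) ] / √(p1(1 − p1) + p2(1 − p2)) }.

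- Tendon exposure, 25% v 5%, p̄ = 0.15: (0.20 × 7.071 − 1.96 × 0.505) / 0.485 = 0.876, so power is 80.9%. The plan states 81%.
- Necrosis, 20% v 5%: 62.4%. The plan states 62%.

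Both figures reproduce. The point does not depend on them, but the same formula can be used for the uncounted events.

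**3. What 50 per arm could say about the uncounted events.** The documents give no rates for them, so the rates below are assumptions.

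- No events in one arm: the exact two-sided 95% upper limit is 1 − 0.025^(1/50) = 7.1%.
- 5% v 15%: SE = √[(0.05 × 0.95 + 0.15 × 0.85)/50] = √(0.175/50) = 0.0592. The 95% half-width is 1.96 × 0.0592 = 11.6 points around a difference of 10, so the interval includes zero.

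| Assumed rates | 95% half-width | Power, normal approximation |
|---|---|---|
| 5% v 5% | 8.5 points | n/a |
| 5% v 10% | 10.3 points | 15.5% |
| 5% v 15% | 11.6 points | 38.3% |
| 5% v 20% | 12.6 points | 62.4% |
| 10% v 20% | 13.9 points | 28.6% |

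For 80% power, the rate in the worse arm would have to be about 19%, 25% or 33% if the other arm's rate is 2%, 5% or 10%.

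**4. Effect on endpoint 2.** Each early loss left uncounted lowers that arm's necrosis rate by 1/50 = 2 points. The planned difference is 20% − 5% = 15 points. The documents do not say how many such losses to expect or in which arm, so the net effect has no known size or sign.

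**The case against.** The strongest reply is that the trial already measures harm. Tendon exposure, necrosis, pain, paresthesia, and loss of motion and strength are donor-site complications, compared by arm with two-sided tests, so a worse result with Integra can be shown. That stands. A reader might infer that the trial can report Integra's benefits but not its harms, or that every endpoint is expected to favour Integra; neither follows. Section 13.0 expects a pigmentation score of 2 with Integra against 1 without, on a scale whose lower total (3 against 5) it presents as the better result.

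A reader might also infer that results are biased towards the arm with more repeat grafts. The documents do not establish this. They describe no re-grafting policy and do not say that replaced grafts count as intact. Endpoint 2 is not restricted to later visits, and photographs at each encounter could catch early necrosis. However, section 5.0 does not say that weeks 1 and 2 are among the photographed visits. No photograph is scheduled between week 2 and month 3, and no text requires a repeat graft to be recorded. The gap is real, but the bias is only possible.

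Three further replies stand in part:

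- The primary objective covers appearance and function and claims no overall safety, and no rule commits the trial to concluding for Integra. The rationale in section 1.0 is nonetheless overall morbidity.
- The added outcomes would be underpowered. That rules out a powered comparison but not a table with intervals. Section 13.0 already keeps a comparison with 16% power because it is simple to collect.
- Section numbers jump from 6.0 to 13.0, and section 6.0 is not a complete list of forms (it does not name strength data either). The finding rests on the public text. An adverse-event section elsewhere would answer part of it.

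**Conclusion.** The narrow point holds. No endpoint, scheduled evaluation or analysis counts donor-site infection, fluid collection, repeat grafting or other unplanned donor-site procedures by arm, and the 1- and 2-week visits have no stated assessment. Graft loss repaired before 3 months may therefore go uncounted under endpoint 2, with unknown effect on the comparison.

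The planned comparisons and their power figures are not undermined by this. What the trial would lack is a systematic by-arm account of harms beyond its own list. That account would be imprecise even if collected: an upper limit of 7.1% with no events in 50, and half-widths of roughly 8 to 14 points over the rates assumed here. It assumes full follow-up of 50 per arm, since the documents give no dropout rate. This is an inexpensive improvement that should be made, not a flaw that invalidates the design.

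**What to change.** In sections 5.0 and 13.0:

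1. Define donor-site infection, fluid collection, repeat graft and other unplanned donor-site procedure. Record each, with date and reason, at every existing visit from surgery to 1 year, including weeks 1 and 2.
2. Report counts by randomised arm, with risk differences and 95% intervals, labelled descriptive and without a power claim.
3. Count a repeat graft done for graft loss as an endpoint 2 event. Repeat grafts done for other reasons should be reported in the new table and not counted as necrosis.
4. Flag every re-grafted subject in the 1-year scar analysis and add a sensitivity analysis. One option is to give these subjects the worst rank in the Wilcoxon rank sum test that the plan already names.

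This changes recording and reporting only. It needs a few REDCap fields and one table, with no added visits, staff or subjects and no change to treatment. The downside is that estimates for the added events will be imprecise, and the report should say so.

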 - a. Range of motion will be measured by resident physicians taking part in the project who will be trained by the occupational therapy team at our institution. The measurements will be taken using electric goniometers so as to standardize the measurements as much as possible.
 - i. Previously reported differences in pre and postoperative range of motion of wrist flexion and extension have ranged from non-statistically significant to about 27 degrees and 22 degrees, respectively.¹
 1. We will expect the difference in wrist flexion and extension in the non-Integra group to be 25 degrees and 20 degrees, respectively.
 2. We will expect the difference in flexion and extension in the Integra group to be 15 and 10 degrees, respectively.[8]
 3. We will again employ two sample t-tests (or Wilcoxon Rank Sum Tests) to test for differences in these angle measurements. Assuming a common standard deviation of five degrees, we will have 99% power to detect a difference in five degrees using a two sample t test.
 - b. Hand strength will be measured by pinch and grip strength dynamometers obtained from the occupational therapy department at our institution. These measurements will be taken at 3 month, 6 month, and 1 year follow up clinic visits.
 - i. Grip strength has been reported to be about a 7kg difference between pre-operative and post-operative measurements, while Pinch strength has been shown to differ by approximately 0.75kg. [29]
 - ii. For the non-integra group, we predict a difference in grip strength of approximately 5kg, while the pinch strength will differ but about 0.75kg
 - iii. For the Integra group, we predict that the difference in grip strength will be approximately 3kg while the pinch strength will differ by approximately 0.25kg.
 - iv. At each time point, we will compare the hand strengths of the Integra and non-Integra groups using two sample t-tests or Wilcoxon Rank Sum Tests as appropriate. Assuming a 5kg grip strength standard deviation in each group, we will have over 99% power to detect differences of 5kg and 7 kg in each group.

The Use of Integra® in Coverage of Radial Forearm Free Flap Donor Site Defect

Comprehensive Cancer Center of Wake Forest University (CCCFWU)

CCCFWU # 99915A

- v. For pinch strength, we assume both groups have a standard deviation of 1kg. To detect a difference 0.75kg, we will have 95% power using a two sample t-test.

7. Wound Contracture and Skin Pliability

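### Blinding is stated only for the 1-year Vancouver rating; for necrosis, tendon exposure, planimetry, motion and strength it is not stated, so these can be judged by people who know the arm

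*Combined protocol and SAP*

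**What the plan says.** Section 5.0 randomizes subjects between a skin graft alone and Integra plus a skin graft. Its only reference to blinding concerns the 1-year visit, where "the Vancouver Scale Assessment will be performed by a Co-Investigator who is blinded".

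The other assessments are described without any statement on knowledge of the arm:

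- **Necrosis and tendon exposure** (Section 5.0): the 3- and 6-month visits include "evaluation of the skin graft and any areas of necrosis or tendon exposure", and the 1-year visit repeats these assessments. The assessor is not named.
- **Photographs and planimetry** (Section 5.0): at surgery and scheduled follow-up, "all subjects will have standardized photographs taken utilizing a custom backdrop and a centimeter scale". On their use: "This will allow us to measure the rate of wound healing, contracture, and rate of skin graft necrosis". On their reading: "The pictures will be analyzed with the SigmaScan planimetry program". The reader is not named.
- **Range of motion** (Section 13.0, item 6a): "Range of motion will be measured by resident physicians taking part in the project". Section 5.0 adds, for the peri-operative period: "Subjects will be evaluated by the occupational therapy team prior to their surgery".
- **Grip and pinch strength** (Section 13.0, item 6b): measured by dynamometer at 3 months, 6 months and 1 year. The assessor is not named.
- **Scar scale before 1 year**: Section 13.0 says "The scores will be taken at the 3,6, and 12 month follow up", whereas Section 5.0 places the blinded rating at 1 year only. Any 3- or 6-month scores therefore have no stated blinding either.

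**The concern.** Deciding whether tendon is exposed or graft is necrotic, tracing a wound edge and reading a goniometer all involve some judgement. The documents set no threshold for calling exposure or necrosis present. Section 13.0 also states which way the investigators hope the result will go: exposure below 5% with Integra. The plastic surgery team follows subjects during admission and arranges their follow-up, so it is plausible that an assessor knows the arm.

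If that knowledge shifts readings in one arm, the treatment comparison is biased, and enrolling more subjects does not remove the bias. By blinding the 1-year scar rating, the plan already accepts that knowledge of the arm can matter. It also already collects standardized images that could be read without the arm.

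**Working it through.** **1. Assessments side by side**

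| Assessment | Who assesses | Blinding |
|---|---|---|
| Vancouver scale, 1 year | Co-investigator | Stated |
| Vancouver scale, 3 and 6 months (Section 13.0 only) | Not named | Not stated |
| Tendon exposure, necrosis | Not named | Not stated |
| Planimetry: wound size, contracture | Not named | Not stated |
| Range of motion | Project residents; occupational therapy peri-operatively | Not stated |
| Grip and pinch strength | Not named at follow-up | Not stated |

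**2. The plan's own figure.** Inputs from Section 13.0: 50 per arm, two-sided 0.05, chi-squared test, exposure 25% against 5%. With pooled proportion 0.15:

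- SE under no difference = √(2 × 0.15 × 0.85 / 50) = 0.0714
- SE under the alternative = √((0.25 × 0.75 + 0.05 × 0.95) / 50) = 0.0686
- Power = Φ((0.20 − 1.96 × 0.0714) / 0.0686) = Φ(0.88) = 80.9%, against 81% stated.

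The figure reproduces. Blinding does not enter it, so there is no corrected power or sample size to report.

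**3. Illustration for tendon exposure.** Assume the same true rate p in both arms, and that a fraction u of exposures goes uncounted in the Integra arm only. The observed Integra rate is then p(1 − u). The false-positive rate is the sum of the binomial probabilities of all pairs of counts (50 per arm) for which the Pearson chi-squared test rejects at 0.05. The 25% rate is the plan's expectation for the graft-only arm, and 12% is the low end of the range it cites. The values of u are assumptions.

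| u | Observed Integra rate, p = 25% | False positives | Observed Integra rate, p = 12% | False positives |
|---|---|---|---|---|
| 0 | 25.0% | 5.1% | 12.0% | 5.4% |
| 10% | 22.5% | 6.1% | 10.8% | 5.7% |
| 20% | 20.0% | 9.3% | 9.6% | 6.9% |
| 33% | 16.8% | 17.6% | 8.0% | 10.0% |
| 50% | 12.5% | 37.1% | 6.0% | 17.6% |

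**4. Illustration for range of motion.** With the plan's SD of 5 degrees and 50 per arm, the standard error of the difference is 5 × √(2/50) = 1 degree. If there is no true difference, an assumed systematic reading bias of 1, 2 or 3 degrees in one arm makes a two-sided t-test reject about 17%, 51% or 84% of the time.

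**The case against.** **Silence is not a statement.** A reader might infer that these assessments are unblinded. The documents do not say so. They do not name who judges exposure or necrosis or who runs the planimetry, and they do not say whether the residents know the arm. One removed passage also cannot be checked, although nothing elsewhere refers to a blinding statement in it. This objection stands, and the point is limited to blinding not being stated.

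**Tendon exposure is not shown to carry the sample size.** A reader might infer that it does, because it is listed first with 81% power. Section 13.0 sets 50 per group and then gives power endpoint by endpoint, naming none as primary. The objective in Section 1.1 is aesthetic quality and functional outcome, and the main aesthetic measure is the one with a blinded 1-year rating. This also stands.

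**There are safeguards.** Residents are trained by occupational therapy and use electric goniometers, and photographs follow a standardized protocol described as validated. These limit reader discretion, but they do not prevent a reading being influenced by knowledge of the arm.

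**The size is assumed.** No figure in the documents supports any rate of one-arm under-counting. At 10% missed the inflation is slight, and 37% is the extreme corner of the table, not an expected value.

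**Reader masking has limits.** It does not address QuickDASH, pain or paresthesia, which subjects report themselves. Motion cannot be read from photographs.

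**Conclusion.** The gap is real and worth closing. Following the plan as written permits several clinician-assessed endpoints to be read with knowledge of the arm, while images that would allow masked reading of some of them are already being collected. The documents support neither a claim that assessors are unblinded nor an estimate of actual bias.

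The size is therefore conditional: about 6% to 37% false positives for tendon exposure at a 25% true rate, and about 6% to 18% at a 12% true rate, if 10% to 50% of exposures are missed in the Integra arm only. The plan's stated power is unaffected. This is a recommended improvement to the design and does not by itself invalidate the trial. If assessors are in practice blinded, a sentence in the protocol saying so would settle the point for those assessments.

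**What to change.** 1. **Photographs.** Label the follow-up photographs by study number only and keep them apart from the intra-operative images, which could show Integra. Run the SigmaScan planimetry and the necrosis reading on the coded images without the arm.
2. **Tendon exposure.** Keep the in-person record at all visits as the endpoint. A photograph-only endpoint could lose exposures that heal between photographed visits, since subjects are also seen at one and two weeks and at the attending physician's discretion. Add a masked reading of the coded photographs as a supporting check.
3. **Protect the existing blinded rating.** If the blinded co-investigator reads the photographs, do it after that subject's 1-year Vancouver score, because graft appearance in earlier images might reveal the arm.
4. **Motion and strength.** Where existing project residents allow, use one who was not at the operation and is not told the arm.
5. **Wording.** For each clinician-assessed endpoint, state who assesses it and whether that person knows the arm. Include any 3- and 6-month scar scores.

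The cost is protocol wording, image coding and reading time: up to 100 subjects × 3 scheduled follow-up visits = 300 sets of follow-up photographs. The documents do not show whether current staffing covers masked motion and strength testing, so that part is conditional. Graft appearance may sometimes reveal the arm, so masking may be incomplete.
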